9.7. Pass/Fail Criteria

9.8. Statistical Termination

No interim analysis will be conducted as statistical outcomes will not change the conduct of the study.

9.9. Statistical Procedure Deviations

Statistical procedure deviations will be reported to the principal investigator and the sponsor. Deviations from the original statistical plan will be explained in the final study report.

9.10. Selection Criteria

All participants who consent, and are fitted with a mask that they attempt to sleep on will be included in the analysis. Please see section 8.10 for information on participant flow throughout the trial.

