6.1. Synopsis

This investigation is a prospective, randomized, non-blinded, cross-over study. The investigation is designed to evaluate the performance, comfort and ease of use of the F&P Full face mask Seal amongst OSA participants. The trial mask seal allocation will be randomized prior to the participant's first visit for the investigation.

This study will be conducted in accordance with ICH/GCP guidelines. No deviation from the protocol will be implanted without prior review and approval of the sponsor except where it may be necessary to eliminate an immediate hazard to a research participant. In such case, the deviation will be reported to the sponsor as soon as possible. In this trial the sponsor and the investigator are the same company however the Sponsor will not be the investigator. To ensure roles are clearly defined and kept independent there will be a delegation of authority log to clearly define each individuals tasks.

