8.2. Controls

The Normal F&P mask seal (trial Seal B) will act as the control for this investigation. Data collected from this mask seal will be compared to the data gathered from the New F&P seal.

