8.4. End Points

8.4.1. Primary Outcomes

- The F&P mask seal is comfortable to use for the participant as measured by the custom questionnaires and recorded during the interviews.
- The mask is easy to use, accepted by the participant and provides adequate treatment for OSA during in-home use, measured via participant feedback and PAP data download (if applicable)

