8.11. Withdrawal Criteria

Participants will be informed that they have the right to withdraw from the study at any time, without prejudice to their medical care, and are not obliged to state their reasons. The participants is informed that they can revert back to their usual therapy during the clinical investigation if they have reason to do so. Additionally the investigator may withdraw a participant at any time for the following reasons:

- Protocol Violation
- Safety concerns
- Serious illness
- Adverse event

The reason for participant discontinuation in the study is to be recorded in the CRF and source document.

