8.12. Number of Trial Subjects

A minimum number of 40-45 F&P full face mask users for OSA therapy will be recruited into this trial.

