9.5. Description of the Statistical Design

Since the trial is to inform product development, no statistical design is required.

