9.6. Sample Size

A minimum of 30 participants will be utilised for each investigation. According to the FDA guidance on Human Factors Engineering, a sample size of 30 will allow a mean of 99% of usability problems to be identified (minimum of 97%)⁷. This is deemed to be appropriate for this investigation as the product is

in feasibility, and the intent is to assess the usability of the user interface to determine further design iterations.

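### Section 9.10 leaves out a participant who is fitted but, because of the seal, attempts sleep on neither seal, so acceptance and ease of use can look better than they were

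*Combined protocol and SAP*

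**What the plan says.** Section 9.10 (Selection Criteria) gives the only visible rule for who is analysed: "All participants who consent, and are fitted with a mask that they attempt to sleep on will be included in the analysis". It then refers to 8.10 for participant flow; most of 8.10 is redacted in the public copy.

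Section 8.4.1 lists as a primary outcome "The mask is easy to use, accepted by the participant and provides adequate treatment for OSA during in-home use", measured through participant feedback and, where applicable, downloaded PAP data.

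On design, 6.1 says "The trial mask seal allocation will be randomized prior to the" first visit, and 8.2 says of the control, the Normal seal: "Data collected from this mask seal will be compared to the data gathered from the New F&P seal".

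On purpose, 9.5 says "Since the trial is to inform product development, no statistical design is required", and 9.6 describes the product as "in feasibility, and the intent is to assess the usability of the user interface to determine further design iterations".

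On the people likely to refuse, 8.12 says "A minimum number of 40-45 F&P full face mask users for OSA therapy will be recruited into this trial", and 8.8 excludes those intolerant to PAP. Section 8.11 lets participants leave at any time without giving a reason, or go back to their usual therapy. It adds: "The reason for participant discontinuation in the study is to be recorded in the CRF and source document".

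**The concern.** Inclusion in the analysis depends on an act that is itself close to the outcome. A participant who has the mask fitted and then will not try to sleep in it because of the seal has answered the question of whether it is acceptable, and the answer is no. Under 9.10 that answer does not enter the analysis if it applies to both seals.

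What is at stake is a descriptive summary of a primary outcome, not a significance level or power, since 9.5 disclaims a statistical design. It still matters for the purpose given in 9.6: a seal-related refusal to sleep in the mask is a usability problem of the kind that the study is meant to bring to light before the next design iteration.

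**Working it through.** **No figure in the plan to reproduce.** The documents give no acceptance rate, refusal rate or non-attempt rate. The sample size figure in 9.6 concerns detection of usability problems and does not bear on this point. The check is therefore a reading of the rule followed by an illustration.

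**Step 1: who is in and who is out under 9.10.**
- Fitted, attempts sleep on both seals: included.
- Fitted, attempts sleep on one seal only: included, because the rule asks for one mask. How the other seal is counted is not visible.
- Fitted, attempts sleep on neither seal: does not meet the rule.

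The sentence does not contain the word *only*. It stands alone under a heading on selection, however, so the natural reading is that anyone who does not meet it is left out.

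**Step 2: direction.** Let N be the number fitted, A the number who accept, and k the number who attempt sleep on neither seal because of the seal. Count these k as non-accepters.
- All fitted: A/N.
- The 9.10 set: A/(N − k).
- Overstatement: A/(N − k) − A/N = A·k / [N(N − k)]. This is never negative, and it is zero when k = 0.

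**Step 3: illustration.** Assumptions, none of them in the documents: acceptance is recorded yes/no, and 80% of those fitted accept. N is set to 40 or 45 (the recruitment figures in 8.12) or 30 (the minimum in 9.6), taking all of them as fitted.

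| N | A | All fitted | k = 1 excluded | k = 2 excluded |
|---|---|---|---|---|
| 40 | 32 | 80.0% | 32/39 = 82.1% (+2.1) | 32/38 = 84.2% (+4.2) |
| 45 | 36 | 80.0% | 36/44 = 81.8% (+1.8) | 36/43 = 83.7% (+3.7) |
| 30 | 24 | 80.0% | 24/29 = 82.8% (+2.8) | 24/28 = 85.7% (+5.7) |

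At N = 40 and k = 1, assumed acceptance of 60%, 70%, 80% or 90% gives +1.5, +1.8, +2.1 or +2.3 points.

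Fixing 80% among those who attempt sleep, instead of among all fitted, changes little. The all-fitted figure is then 0.80 × 39/40 = 78.0% for k = 1 and 0.80 × 38/40 = 76.0% for k = 2, an overstatement of 2.0 and 4.0 points.

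**Step 4: the comparison between seals.** The effect depends on which seals the refusers were fitted with, which the visible text does not say. Take N = 40, two refusers, and 32 accepters of each seal.
- Both refusers fitted with both seals and refusing both: 32/40 − 32/40 = 0 with all fitted, and 32/38 − 32/38 = 0 under 9.10. No change.
- Both fitted with New only, refusing it and leaving before Normal is fitted: 32/40 − 32/38 = 80.0% − 84.2% = −4.2 points with those fitted with each seal as denominator, against 0 under 9.10.

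The same exclusion can leave the New-minus-Normal difference alone or shift it, so no size or direction is claimed for it.

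**The case against.** **Acceptance may not be a proportion.** Section 6.5 calls the questionnaire data qualitative, and no visible section defines acceptance as yes/no. This stands: the percentages only illustrate. The direction needs less, namely that a seal-related refusal counts as unfavourable.

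**The set fits a home-use question.** Section 8.4.1 refers to in-home use, and someone who never tries to sleep has no night to report. This is right for comfort ratings and for PAP and leak data, where the attempted-sleep set should stay. It is weaker for acceptance, which can be refused without a night's use.

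**Fitting is also after allocation.** Under 6.1 the order is fixed before the first visit, so a set of fitted participants is no more an as-randomised set than the one in 9.10. This stands. The point rests on the link between attempting sleep and the outcome, not on its timing after randomisation.

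**Refusals may be rare.** Recruits already use a full face mask, PAP-intolerant people are excluded, and the case requires refusing the control seal too, or leaving before it is tried. This stands and holds the severity down. No visible test or threshold depends on the result.

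**Stronger readings that the documents do not support.** A reader might infer that 9.10 favours the New seal over the Normal seal; the two fitting patterns worked through above show that this does not follow. A reader might also infer that the plan has no rule for a participant who refuses one seal and tries the other. That cannot be said: the detail of 8.10 and Appendices C and D are redacted, Appendix B is not shown, and 8.5, 8.6 and 9.7 are bare headings in this copy. A rule may sit in any of them, so this is a query only.

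**Conclusion.** The point holds, at low severity. Followed as written, 9.10 leaves out a fitted participant who, because of the seal, attempts sleep on neither seal, and the acceptance and ease-of-use results are then unchanged or too favourable. The size is unknown and may be zero. If acceptance is yes/no and about 80% of 40 fitted participants accept, each such exclusion adds about 2 points. That figure assumes the response format, the acceptance rate and the number of refusers, and it assumes that a seal-related refusal counts as non-acceptance. Non-attempts for illness or other reasons unrelated to the seal are not part of the point.

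**What to change.** In 9.10, for acceptance and ease of use only:

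- Include every consented participant fitted with at least one seal.
- Count a seal-related refusal, or a seal-related failure to attempt sleep, as not accepted for the seal concerned.
- Show seals never fitted as a separate category, not as refusals.
- Report the counts and reasons by seal and by order, with a line for reason not given, since 8.11 does not oblige participants to state one.

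Keep the attempted-sleep set for comfort ratings and for PAP and leak data. If a redacted section already says how a single refused seal is counted, a cross-reference in 9.10 is enough; if not, the second item above settles it.

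The cost is a few sentences, one extra table, and a note by staff of whether a refusal was seal-related. Section 8.11 already has the reason for discontinuation recorded. The reported acceptance figure may be lower.

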10.3. Reporting Adverse Events

Any serious AE, due to any cause, that occurs during the study period, must be reported immediately (within the next business day) by telephone to the sponsor. In addition to the initial telephone report, a Serious Adverse Event form must be completed and sent via facsimile to the sponsor. All serious AE's must also be recorded on the AE page of the CRF. Additionally, all serious AE's must be reported to the Independent Review Board (IRB) as per the IRB's requirements.

10.4. Early Termination

The study may be discontinued at any time on the advice of the responsible investigator on the basis of new information regarding safety or efficacy. Additionally, the study may be terminated if progress

is unsatisfactory. The following documentation is required if the appropriate party terminates a clinical trial.

10.5. Investigator

If the investigator terminates or suspends a trial without prior agreement of the sponsor, the investigator should inform the institution, where required by the applicable regulatory requirements and the investigator/institution should promptly inform the sponsor and the IRB, and should provide the sponsor and the IRB a detailed written explanation of the termination or suspension.

10.6. Sponsor

If the sponsor terminates or suspends a trial, the investigator should promptly inform the institution, where required by the applicable regulatory requirements, and the investigator/institution should promptly inform the IRB and provide the IRB a detailed written explanation of the termination or suspension.

16. Appendix C: [REDACTED]

17. Appendix D: [REDACTED]
